9.3 Serious Adverse Events (SAE)

9.3.1 Assessment of Seriousness

Seriousness refers to the outcome of an adverse event. Seriousness is determined by both the PI and the Sponsor Medical Monitor. If either PI or Sponsor Medical Monitor determines an event to be serious, it will be classified as such. If any of the following outcomes are present then the adverse event is serious:

- **It results in death** (i.e., the AE caused or led to the fatality). Serious does not describe an event that hypothetically might have caused death if it were more severe.
- **It was immediately life-threatening** (i.e., the AE placed the subject at immediate risk of dying). It does not refer to an event that hypothetically may have led to death if it were more severe.
- **It required inpatient hospitalization or prolonged hospitalization** beyond the expected length of stay. Hospitalizations for scheduled treatments and elective medical/surgical procedures related to a pre-existing condition that did not increase in severity or frequency following receipt of study injection, are not serious by this criterion. Hospitalization is defined as either a hospital admission or an emergency room visit for a period greater than 24 hours.

- **It resulted in a persistent or significant disability/incapacity** (i.e., substantial reduction of the subject's ability to carry out activities of daily living).
- **It resulted in a congenital anomaly or birth defect** (i.e., an adverse finding in a child or fetus of a subject exposed to the study vaccine prior to conception or during pregnancy).
- **Other medically important conditions** that may not result in death, threaten life, or require hospitalization (i.e., the AE does not meet any of the above serious criteria) may be considered a serious adverse event when, based on appropriate medical judgment, they may jeopardize the subject and require medical or surgical intervention to prevent one of the serious outcomes listed in these criteria (e.g., allergic bronchospasm requiring intensive treatment in an emergency room or at home, blood dyscrasias or convulsions that do not result in hospitalization, or the development of drug dependency or drug abuse).

A serious adverse event is an adverse event meeting the outcome criteria for seriousness regardless of relationship to the study injection.

When an adverse event is judged related to an investigational product and is serious and unexpected, it is a SUSAR and subject to expedited reporting.

9.3.2 Procedures to be Followed in the Event of Abnormal Laboratory Test Values or Abnormal Clinical Findings

Investigation, treatment, follow-up, and medical referral of all adverse events will be determined by the investigator using his/her best medical judgment and according to local clinical practice guidelines.

Laboratory values that are abnormal based on the toxicity tables will be reported as an AE. In the event a subject experiences an AE or injection site reaction that is still present at the end of the subject's participation in the study, the subject must be followed until resolution of the event or until the event or abnormality resolves or stabilizes to the investigator's and/or sponsor's satisfaction. Follow-up procedures, evaluations, and outcomes will be recorded on the subject's eCRFs.

9.4 Reporting Procedures

The PI (or designee) must report immediately (within 24 hours) any occurrence of SAEs or other reportable events described in this section to IDRI Pharmacovigilance.

9.4.1 Serious Adverse Events

Serious AEs will be collected from the time of the first study drug administration until the final study visit. Serious AEs that are related to the investigational drug and continue beyond the normal collection period (i.e., are ongoing at the time a subject exits the study) will be followed until resolution or until stabilized with sequelae. Serious AEs that begin after the subject's

participation in the study is complete, but that the Investigator considers to be related to study drug, may be reported at any time.

The Investigator or clinical site personnel should notify IDRI Pharmacovigilance of all SAEs, regardless of relationship to the investigational drug, within 24 hours of clinical site personnel becoming aware of the event. The Investigator will provide the initial notification by sending a completed "RAE Report Form," which must include the Investigator's assessment of the relationship of the event to investigational drug, and must be signed by the Investigator.

In addition, notification is sent by the clinical site to the IRB as required.

Follow-up information, or new information regarding an ongoing SAE, must be provided promptly to IDRI Pharmacovigilance.

All SAE reports should be sent to the following contacts:

In case of a serious adverse event, the Principal Investigator will send a report within 24 hours of notification to:

IDRI Pharmacovigilance
[name]
[name]
E-mail: [contact]
[contact]
[contact]

IDRI will ensure notification of all serious adverse events as soon as possible, but no later than 24 hours after learning of an event to DMID PVG below:

DMID Pharmacovigilance Group
Clinical Research Operations and Management Support (CROMS)
[name]
[name]
SAE Hot Line: [contact] (U.S.) or [contact] (outside U.S.)
SAE FAX [contact] (U.S.) or [contact] (outside U.S.)
SAE Email Address: [contact]

IDRI is responsible for submitting the SAE to DMID as soon as possible, but no later than 24 hours after learning of an SAE.

The DMID Medical Monitor and the DMID Clinical Project Manager will be notified of the SAE by the DMID Pharmacovigilance Group. The DMID Medical Monitor will review and assess the SAE for potential impact on study subject safety and protocol conduct.

The Independent Safety Monitor will receive copies of all correspondence between the Sponsor and FDA for SAEs.

The sponsor is responsible for determining regulatory reporting requirements for SAEs.

9.4.2 Regulatory Reporting

The sponsor will report all suspected unexpected serious adverse reactions (SUSARs) to the FDA within 7 or 15 days of receipt of the report of the event, depending on the nature of the SUSAR. In addition, all other SAEs and PIMMCs will be reported annually to the FDA in a dedicated tabulation by MedDRA coding term and relationship to study vaccine.

9.4.3 Reporting Other Adverse Events (if applicable)

The investigator must report the following events by scanning and emailing, or faxing, the appropriate form to the Sponsor Medical Monitor or designee within one business day of becoming aware of the event:

- Protocol violation affecting the safety of a participant or involving the study injection process (Reportable Adverse Event Form)
- Any event that, according to the protocol or in the opinion of the investigator, precludes further administration of the study injections (Reportable Adverse Event Form)
- Pregnancy (Pregnancy Alert Report Form)

9.4.4 Reporting of Pregnancy

If a participant becomes pregnant during the study, she will not receive any further study injections but should be encouraged to continue in the study for safety follow-up. Follow-up should continue for pregnancy outcome including premature terminations, and data are to be included in the safety reports.

The health status of the mother and child, the date of delivery, and the child's sex, birth weight, and parity should be reported to the Sponsor. Pregnancy will not be recorded as an adverse event. However, if the pregnancy results in a miscarriage or a planned termination, the event (spontaneous abortion or elective abortion) will be reported as an adverse event or serious adverse event per the investigator's judgment (e.g., if it was a medically important or life-threatening event that meets the definition of a serious adverse event).

A congenital anomaly or birth defect (i.e., an adverse finding in a child or fetus of a participant exposed to the study vaccine before conception or during pregnancy) must be reported as a serious adverse event.

9.5 Type and Duration of Follow-up of Subjects after Adverse Events

Adverse events will be considered resolved when the condition returns to normal or returns to the participant's baseline status as established on Study Day 0, or when the condition has stabilized with the expectation that it will remain chronic.

The investigator will continue follow-up on adverse events, including laboratory abnormalities and solicited adverse events, until the event has resolved, is otherwise satisfactorily explained, or the participant completes the study.

Follow-up for serious adverse events must continue until resolution and the outcome reported, even if this extends beyond the serious adverse event reporting period (i.e., after the final study visit). For analysis purposes, the outcome for serious adverse events will be determined on the final study visit.

Outcome of all adverse events will be classified as one of the following:

- Resolved
- Resolved with sequelae
- Death

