Potential immune-mediated medical conditions (PIMMCs): FDA requires monitoring for specified known or suspected autoimmune disorders when testing novel adjuvants. PIMMCs will be recorded on the AE form and reported to IDRI Pharmacovigilance regardless of their attributed relationship to study injections. PIMMCs consist of any of the diagnoses listed in [Appendix 6](#) reported in study injection recipients at any time during the study period or after completion of the study.

All adverse events (including PIMMCs) will be reported on the Adverse Event eCRF using a recognized medical term or diagnosis that accurately reflects the event. Adverse event evaluations will be reviewed by the PI or by a designated medically qualified practitioner. Adverse event eCRF pages are to be completed by members of the study team designated in writing by the PI. The onset and resolution dates of the event and action taken in response to the event will be documented. All adverse events must be followed until resolution or stabilization is demonstrated. The resolution date will be recorded on the eCRF as the last date on which the participant experienced the adverse event. If the subject cannot recall the date of resolution, then the resolution date will be the visit date on which the study staff determines the AE to be resolved.

Adverse events that are still present at the end of the trial should be recorded as ongoing and be followed until resolved or considered stable. Information recorded on the eCRF must be substantiated in the source documents. If an adverse event evolves into a condition that becomes “serious,” it will be designated as serious on the Adverse Event eCRF and an SAE Report will be completed.

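### Protocol 9.5 counts a stable chronic condition as resolved and has no outcome for an unresolved event, contrary to 9.2.1; a persistent SAE or PIMMC may be coded as resolved or have no valid code

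*Protocol*

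**What the plan says.** Section 9.5 of the protocol does four things that bear on this point.

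- It defines resolution. An event is resolved when it returns to normal or to the Day 0 baseline, "or when the condition has stabilized with the expectation that it will remain chronic".
- It sets a closed list: "Outcome of all adverse events will be classified as one of the following", followed by Resolved, "Resolved with sequelae" and Death. Nothing on the list describes an event that has not resolved.
- It fixes a time point: "For analysis purposes, the outcome for serious adverse events will be determined on the final study visit". The sentence before it requires SAE follow-up to continue to resolution even after that visit.
- It lets follow-up of other adverse events run "until the event has resolved, is otherwise satisfactorily explained, or the participant completes the study".

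Other sections differ. Section 9.2.1 states: "Adverse events that are still present at the end of the trial should be recorded as ongoing", with follow-up until they are resolved or considered stable. It also dates resolution as the last day on which the participant experienced the event. Section 7.11 (early termination) follows ongoing events and PIMMCs to resolution or to an established stable chronic condition. Section 9.4.1 follows related SAEs that are open at exit to resolution or to stabilisation with sequelae. Under section 9.3.2, for an event still present at the end of participation, "the subject must be followed until resolution of the event" or until it stabilises.

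**The concern.** PIMMCs and SAEs are collected through the Day 421 contact, and this is the first trial of the single-vial presentation. Appendix 6 contains diagnoses such as multiple sclerosis and type I diabetes, which can be expected to persist once they appear. These are the conditions that the chronic clause in 9.5 reaches. Whether such an event persisted is something a safety reader will want to know, and in a trial of 48 subjects one event's outcome can matter to the reader.

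If 9.5 is applied as written, a lasting condition can carry a resolved code. If 9.2.1 is applied, the same condition is ongoing. An SAE that is still evolving at the final visit must be given an outcome for analysis that the list does not contain.

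**Working it through.** The documents give no figure to reproduce, and no calculation is involved. The check sets the rules side by side for the states a surviving subject's event can be in at the final visit, and then asks which planned outputs use the outcome code.

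**Step 1. Outcome at the final visit**

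| State of the event | Under 9.5 | Under 9.2.1 |
|---|---|---|
| (a) Back to normal or baseline | Resolved | Resolved, dated to the last day experienced |
| (b) Still present, stable, expected to be chronic | Counts as resolved; coded Resolved or Resolved with sequelae, with no rule for choosing | Recorded as ongoing |
| (c) Still present, not stable | No code applies | Recorded as ongoing |

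The sections agree on (a) and conflict on (b) and (c).

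**Step 2. Resolved versus stable.** Sections 9.2.1, 7.11 and 9.4.1 each name resolution and stabilisation as alternative end states. Section 9.5 folds the second into the first. The resolution date in 9.2.1 shows the difficulty: a condition in state (b) is still being experienced, so it has no last day to enter.

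**Step 3. Section 9.5 on its own terms.** It expects some SAEs to be open after the final visit, and it lets follow-up of other events stop at study completion without resolution. Both rules foresee state (c), yet the outcome list has no entry for it. The gap would therefore exist even without 9.2.1.

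**Step 4. Which outputs use the code**

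- Primary outcome measures (protocol 3.2.1): numbers of subjects with reactions or events, and the number of related SAEs. Outcome is not used.
- SAP 7.2.2.2: number and percentage of subjects with at least one event, covering all events, related events, SAEs and PIMMCs, with further summaries by injection, severity and relationship. Outcome is not used.
- Annual regulatory tabulation (protocol 9.4.2): by MedDRA term and relationship. Outcome is not named.
- SAP Listings 16.7 (adverse event description) and 16.10 (deaths, SAEs and PIMMCs), and narratives: outcome could appear. The SAP does not specify the listing columns.

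The conflict therefore reaches the outcome field and whatever displays it, and no incidence count.

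**Step 5. End of follow-up, a separate matter.** For a non-serious event, 9.5 allows follow-up to stop when it "is otherwise satisfactorily explained, or the participant completes the study". Sections 9.2.1 and 9.3.2 continue follow-up of events still present at the end until they resolve or stabilise, and 7.11 does the same after early termination. The sections differ in practice for state (c). For SAEs, 9.5 continues follow-up of every SAE to resolution as it defines that term, whereas 9.4.1 speaks of related SAEs and gives stabilisation with sequelae as its own end point.

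**The case against.** The strongest reply is that little depends on the outcome code. No endpoint and no planned summary uses it, and a PIMMC is listed by diagnosis whatever its outcome, so a case of multiple sclerosis would not be hidden. That stands, and it limits the point to the recording and display of outcome.

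A second reply is that Resolved with sequelae can flag a lasting effect. This stands in part. It may suit some stable cases, but it still labels a persisting disease as resolved, 9.5 does not say when to use it, and it does not fit an event that is still active and unstable.

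A third reply is that 9.2.1 already tells the site what to record, and that the eCRF, which is not among the documents, may already have an ongoing field. That is possible. It would make the coding correct in practice and leave 9.5 wrong on paper.

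Fourth, section 2.3.1 reports no serious events and no events of special interest (since renamed PIMMCs) in three earlier trials of the vaccine, so few or no SAEs or PIMMCs may be affected. This is fair. The documents give no PIMMC rate from which to estimate a number.

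A reader might go further and infer that persistent SAEs and PIMMCs will be reported as recovered, so that lasting harm is concealed. The documents do not support that. It assumes that 9.5 overrides 9.2.1, it passes over the sequelae code, and it treats unstable events as resolved when they are in fact uncodable. Nor does 9.3.2 contradict the outcome list: it governs how long follow-up lasts and names no outcome.

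**Conclusion.** The contradiction is real and lies in the wording. Section 9.5 counts a stabilised chronic condition as resolved and offers no outcome for an unresolved event, while 9.2.1 requires such an event to be recorded as ongoing, and 7.11 and 9.4.1 keep the two end states apart. Depending on which section the site followed, a persistent SAE or PIMMC may have been coded Resolved or Resolved with sequelae. An event still unstable at the final visit has no valid code under 9.5, although that is where 9.5 fixes the SAE outcome for analysis. Ordinary adverse events still open at exit are affected in the same way.

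The size is limited. Adverse event, SAE and PIMMC incidence, and all primary outcome counts, are unchanged. What can be wrong is the outcome shown for individual events, for example in Listings 16.7 and 16.10 or in narratives. This rests on two things the documents do not settle: whether the eCRF already carries an ongoing code, and whether those outputs display outcome. The number of affected events cannot be estimated from the documents. The point is worth correcting but does not threaten the primary results.

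**What to change.** 1. Add a not resolved/ongoing category to the outcome list in 9.5, and to the adverse event eCRF if it is not already there.
2. Record conditions that are stable but expected to remain chronic under that category, not as resolved.
3. Show SAE and PIMMC outcome at the final visit with the new category included.
4. SAP section 1 states that the safety analysis has already been performed. Check each event that was open at the subject's last visit, or that was closed because it had become chronic. Correct the affected listings and narratives, or footnote them.
5. Separately, reconcile 7.11, 9.2.1, 9.3.2, 9.4.1 and 9.5 on when follow-up ends. This review does not say which rule is right. Deleting the chronic clause from 9.5 alone would not be enough: 9.5 follows SAEs until resolution, so a chronic SAE would be left without a follow-up end point in that section. The outcome code and the end of follow-up should be stated as two separate rules.

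The cost is protocol wording, at most one eCRF code, and a retrospective check of the open and chronic events. Items 1 to 4 need no extra visits.

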9.6 Halting Rules

9.6.1 Rules for Discontinuing Study Injection in an Individual Subject

Administration of additional study injections will be discontinued for an individual if he/she has any of the following reactions:

- Changes in laboratory parameters that meet Grade 3 severity.
- High fever (oral temperature $\geq 102.2^{\circ}\text{F}/39^{\circ}\text{C}$) within 1 week following study injection associated with constitutional symptoms and not attributable to another cause.
- Severe injection site reactogenicity that involves Grade 3 local pain, induration, or erythema.

9.6.2 Rules for Suspension of the Entire Study

The study will be immediately suspended (paused) and no additional study injections administered, pending review and discussion of all appropriate safety data by the SMC, if one or more subjects in any treatment group experience any of the following adverse events:

- Anaphylaxis or bronchospasm within 4 hours of study injection indicative of an immediate hypersensitivity reaction to the vaccine and not attributable to another cause.
- Any systemic rash, including but not limited to urticaria, generalized petechiae, or erythema multiforme, not attributable to another cause.
- Tissue necrosis at the study injection site.
- Any other serious adverse event deemed to be possibly, probably, or definitely relatable to the study injection by the PI or Sponsor Medical Monitor, based on close temporal relationship or other factors.

The study will also be immediately suspended (paused) and no additional study injections administered pending review and discussion of all appropriate safety data by the SMC if three or more subjects experience the following AEs determined to be related to study injection:

- Changes in laboratory parameters that meet Grade 3 severity.
- High fever (oral temperature $\geq 102.2^{\circ}\text{F}/39^{\circ}\text{C}$) within 1 week following study injection associated with constitutional symptoms and not attributable to another cause.
- Severe injection site reactogenicity that involves Grade 3 local pain, induration, or erythema.

Study suspension or termination will only apply to additional study injections. Subjects for whom their study injections are discontinued will remain in limited visit follow-up for safety evaluations and immunology blood draws.

9.7 Safety Oversight (ISM plus SMC)

9.7.1 Independent Safety Monitor (ISM)

The ISM is a physician with relevant expertise whose primary responsibility is to provide independent safety monitoring in a timely fashion. The ISM will review SAEs and other AEs as needed and provide an independent assessment to DMID. Saint Louis University will have an ISM with experience in infectious diseases or internal medicine.

9.7.2 Safety Monitoring Committee (SMC)

This clinical trial will utilize an SMC, which will be comprised of an independent group of experts with experience with early phase clinical research studies. The primary responsibility of the SMC is to monitor subject safety. The SMC is external to DMID and composed of at least three voting members. The SMC will consist of members with appropriate expertise to contribute to the interpretation of the data from this trial. Committee activities will be delineated in an SMC charter that will delineate membership, responsibilities, and the scope and frequency of data reviews. The SMC will operate on a conflict-free basis independently of the study team.

Subsequent to the Organizational Meeting, the SMC will review and discuss safety data at the following milestones:

- Ad hoc meeting will be conducted:
 - If study halting criteria are met as described in [Section 9.6](#)
 - At the request of DMID to review a potential safety concern identified by the PI, the Sponsor's Medical Monitor, DMID MM or ISM
- Final review meeting: 6 to 8 months after clinical database lock to review the cumulative unblinded safety data for the study. The data will be provided in a standard summary format. The SMC may be asked to provide recommendations in response to questions posed by DMID.

The SMC will have access to unblinded data during its closed session, if applicable. After its assessment, the SMC will recommend continuation, modification, or termination of the clinical trial. Additionally, data management alerts will be implemented and monitored to determine if any of the halting rules described in [Section 9.6](#) are met.

If any of the halting rules are met following the first study injection, the study will not proceed with the remaining enrollment or study injections without a review by and recommendation from the SMC to proceed.

The DMID Medical Monitor and Clinical Project Manager will review the SMC recommendations and will document what actions DMID recommends be implemented by the study team. The Sponsor will receive the recommendations and will be responsible for responding to the SMC and DMID regarding any actions that were recommended and will not be implemented.

